APPENDIX VII: CIP SUMMARY	
APPENDIX VIII: REFERENCES	37

COMPLIANCE STATEMENT:

This clinical investigation will be conducted in accordance with this Clinical Investigation Plan, the Declaration of Helsinki and the applicable regulatory requirements (such as, 21 CFR Part 50, 21 CFR Part 56,21 CFR Part 812, 21 CFR Part 54, and 21 CFR Part 11and 45 CFR part 46). The conduct of the clinical investigation will be approved by the Food and Drug Administration (FDA) and the appropriate Institutional Review Board (IRB) of the respective investigational site.

1.0 INTRODUCTION

Spinal cord stimulation (SCS) has been shown to be effective for relieving intractable chronic pain. However, a portion of patients who initially succeed with SCS will eventually lose their therapeutic benefit. Reliable methods have not been identified for restoring neuromodulation benefit to this underserved population, so additional research is required. This study will prospectively observe subjects who utilize Abbott neurostimulation devices after failing to sustain pain relief with their previous SCS system. The effectiveness of Abbott systems in restoring neuromodulation benefit will be evaluated over the course of a two-year follow-up.

This clinical investigation will be conducted in accordance with this clinical investigation plan (CIP). All Investigators involved in the conduct of the clinical investigation will be qualified by education, training, or experience to perform their tasks and this training will be documented appropriately.

1.1 Background and Rationale

1.1.1 Background

Spinal cord stimulation involves the application of electrical stimulation to the large, myelinated fibers of the dorsal column via electrical leads placed in the epidural space. SCS has been used successfully to help manage a variety of pain conditions including diabetic neuropathy,¹ failed back surgery syndrome,²⁻⁴ complex regional pain syndrome,^{5,6} phantom limb pain,⁷ ischemic limb pain,⁸ as well as postherpetic neuropathic back and leg pain showed that SCS reduces pain, improves quality of life, reduces analgesic use, allows some patients to return to work, and may result in significant cost savings over time with minimal significant adverse events.¹⁰ However, not all patients continue to receive benefit from SCS over time. A recent retrospective review of the MarketScan database found that of the 8727 patients implanted, 805 (9.2%) had the devices explanted. Patients who were explanted incurred 2.65 times more total cost than their counterparts who retained the SCS system.¹¹ While the MarketScan database does not provide the reason for explant, others have examined the question with smaller cohorts.

Explants occur for a variety of reasons, the most common being loss of therapeutic effect. In a review of 352 patients who had an SCS explant, Pope et al. found that the top three reasons for explant were lack/loss of efficacy (43.9%), complication (20.2%), and a need for MRI (19.4%). Importantly, 71.8% of all explants occurred within the first 30 months.¹² In a similar study by Van Buyten et al., the primary reasons for explant across 955 devices were inadequate pain relief (50.5%), infection (24.7%), and internal pulse generator (IPG) failure (11.8%).¹³ The overall explant rate in this study was 19.5% and the majority of explants due to inadequate pain relief occurred within the first two years.¹³ Finally, Hayek et al. reviewed 56 explants in 234 patients (23.9%) with the top explant drivers being loss of therapeutic effect (41.0%), infection (17.8%), and IPG discomfort (14.3%).¹⁴ Across these three studies, loss of efficacy comprised 40% - 50% of all SCS explants. In addition to the documented explant rate, it is reasonable to assume that some patients have lost efficacy, but do not want to go through the effort of having their device removed. This population of "virtual explants" is difficult to quantify and, to our knowledge, has not been estimated in the literature.

The underlying reason for therapeutic failure after initial success is unknown. It is possible that neural plasticity may cause the nervous system to habituate to the stimulation, diminishing or eliminating benefit.¹⁵ It is also possible that the loss of benefit is a complex interaction of physical and mental factors such as anxiety and depression, which have been shown to affect other treatments for chronic pain.¹⁶ While the cause is unknown, several attempts have been made to restore neuromodulation efficacy for

failed SCS patients through "stimulation holidays" whereby the stimulator is temporarily turned off for a period of time, or by switching to another form of stimulation.¹⁷

Stimulation holidays, where the device is shut off for 6 weeks, are believed to allow any neural adaptation to reverse, restoring efficacy when the device is reactivated. However, little evidence supports this method.^{15,17} Recent case studies have shown that changing the stimulation waveform or stimulation target are possible solutions for stimulation tolerance. Ten of 16 patients switching from high-frequency to tonic stimulation,¹⁸ and 3 of 3 switching from tonic to BurstDR stimulation reached acceptable levels of pain relief.¹⁹ Additionally, 2 of 2 patients were successful in restoring their pain relief after switching from traditional SCS to dorsal root ganglion (DRG) stimulation.²⁰

1.1.2 Rationale for Conducting this Clinical Investigation

This study will examine the utility of Abbott neurostimulation devices for restoring therapeutic benefit from neuromodulation therapy. These devices include programming the BurstDR waveform in an enabled implantable pulse generator (IPG), and dorsal root ganglion stimulation (Proclaim DRG). The BurstDR waveform offers a unique mechanism of action that may explain why it can restore efficacy where tonic stimulation has failed. While all forms of SCS activate the lateral pain pathway, which is responsible for the sensory aspects of pain, only BurstDR has been shown to activate the medial pain pathway which is responsible for the affective components.²¹ It is this medial activation that may allow BurstDR to succeed despite psychological factors such as catastrophizing and depression. Additionally, it is possible that BurstDR may be less susceptible to habituation because it more closely mimics natural thalamic firing.²²

Several different methods of implementing BurstDR may be included in this investigation to account for a range of possible existing systems and patient needs. It can be implemented by reprogramming a BurstDR-capable device, connecting a BurstDR-capable IPG to existing leads with an adapter or compatible header, or through full system replacement.

While traditional SCS applies stimulation to the dorsal horn of the spinal cord, DRG stimulation targets a bundle of sensory nerve cell bodies just outside of the spinal cord known as the dorsal root ganglion. This form of stimulation has been shown to make it easier to achieve pain-paresthesia overlap, provide consistent stimulation irrespective of body position, and produce paresthesia with a lower current than traditional SCS.²³ A recent RCT found that DRG was superior to SCS in providing pain relief for individuals with complex regional pain syndrome (CRPS).²⁴ Using DRG stimulation as a replacement or supplement to SCS may ensure reliable coverage of the entire painful area and improve pain outcomes.

This is the first prospective investigation designed to evaluate the effectiveness of Abbott neurostimulation devices for restoring pain relief in patients with waning or failed therapy.

2.0 CLINICAL STUDY OVERVIEW

2.1 Clinical Study Objectives

The objectives of this study are to evaluate the effectiveness of Abbott neurostimulation devices in restoring pain relief, improving quality of life, and reducing related medication use for patients with failed SCS.

2.2 Devices to Be Used in the Clinical Investigation

Any market-released Abbott BurstDR-capable or DRG neurostimulation device may be used in this study along with its relevant accessories. This study allows for the inclusion of future iterations of Abbott's neurostimulation systems and expanded indications as they receive approval from the applicable country regulatory authority.

2.2.1 Indications for Use

Indications for use for each neurostimulation device/system are detailed in the country-specific individual Instructions for Use (IFU) document.

2.2.2 Description of the Study Devices

Please refer to the country- and device-specific IFU for additional information regarding the devices used in this clinical investigation.

2.2.3 Device Handling

The Sponsor requires all products to be stored according to the appropriate labeling and IFU as per standard practice at each center.

3.0 CLINICAL INVESTIGATION DESIGN

This study is a prospective, multi-center, open-label, post-market study designed to evaluate the effectiveness of Abbott neurostimulation devices in restoring pain relief for patients who no longer receive adequate therapeutic benefit from SCS. The Investigator will select the most appropriate BurstDR or DRG implementation method according to their standard of care.

A trial of BurstDR or DRG may be performed as deemed appropriate by the Investigator. This includes the option for multiple trials to test both BurstDR and DRG therapy. Similarly, the permanent implementation method will be performed as deemed appropriate by the Investigator.

This clinical investigation will enroll up to 100 patients at up to 40 sites in the US. Subject enrollment is expected to be completed within 12 months; subjects will be followed for 24 months after permanent implementation.

The clinical investigation has been designed to involve as little pain, discomfort, fear, and any other foreseeable risk as possible for subjects. Refer to the Risks Analysis section of this investigation plan for details.

3.1 Study Procedures and Follow-up Schedule

3.2 Measures Taken to Avoid and Minimize Bias

An independent Clinical Events Committee (CEC) will adjudicate all serious device/procedure related adverse events.

3.3 Suspension or Early Termination of the Clinical Investigation

While no formal statistical rule for early termination of the clinical investigation for insufficient effectiveness of the study devices is defined, the Sponsor reserves the right to discontinue the clinical investigation at any stage or reduce the follow-up period with suitable written notice to the Investigator. Possible reason(s) may include, but are not limited to:

- Unanticipated adverse device effect (UADE) occurs and it presents an unreasonable risk to the participating subjects
- An oversight committee (e.g., Steering/Executive Committee, Data Monitoring Committee) makes a recommendation to stop or terminate the clinical investigation (such as higher frequency of anticipated adverse device effects)
- Further product development is cancelled

Should the clinical investigation be discontinued by the Sponsor, subjects will be followed per routine clinical practice with device/procedure related AEs reported to the Sponsor as per vigilance/commercial reporting requirements. The Investigator shall return all clinical investigation materials (including devices) to the Sponsor, and provide a written statement to the IRB/EC (if applicable). All applicable clinical investigation documents shall be subject to the same retention policy as detailed in [Section 11.5] of the CIP.

A Principal Investigator, IRB/EC or regulatory authority may suspend or prematurely terminate participation in a clinical investigation at the investigational site(s) for which they are responsible. The Investigators will follow the requirements specified in the Clinical Trial Agreement.

If the Sponsor suspends or prematurely terminates the clinical investigation at an individual site in the interest of safety, the Sponsor will inform all other Principal Investigators.

If suspension or premature termination occurs, the Principal Investigator or authorized designee will promptly inform the enrolled subjects at his/her site, if appropriate, and return patients to their standard medical treatment.

4.0 ENDPOINTS

- Numerical rating scale (NRS) for pain intensity
- Patient reported pain relief
- Patient satisfaction
- Physician satisfaction
- PROMIS-29
- Pain Catastrophizing Scale (PCS)
- Pain Vigilance and Awareness Questionnaire (PVAQ)
- Pain condition-related medication usage

5.0 SUBJECT SELECTION AND WITHDRAWAL

5.1 Subject Population

This clinical investigation will enroll male and female subjects with chronic pain who are considered to have failed therapy with their existing SCS system. Subjects must meet all eligibility criteria and provide written informed consent prior to conducting any investigation-specific procedures not considered standard of care.

5.2 Subject Screening and Informed Consent

5.2.1 Subject Screening

Potential patients presenting at the clinical sites will be fully informed about the clinical investigation, following the established Informed Consent process (described in [Section 5.2.2]). Once a duly dated and signed Informed Consent form is obtained, the clinical investigation-specific screening procedures may begin.

Subjects must be screened for clinical investigation eligibility by a member of the site's clinical investigation team previously trained to the CIP, and will be recorded in a site-specific screening log.

In case the subject does not meet all inclusion criteria, or meets any of the exclusion criteria, the subject is considered a screening failure. The Principal Investigator or the delegated clinical investigation personnel will record the screening failure in the hospital records and on a screening log as required.

Patients meeting general inclusion criteria and no exclusion criteria will be asked to sign an Informed Consent form if they wish to participate in the clinical investigation. These patients will also be recorded in the screening log.

Subject data will be collected following enrollment into the study.

5.2.2 Informed Consent

The Investigator or his/her authorized designee (if applicable) will conduct the Informed Consent process, as required by applicable regulations and the center's IRB/EC. Special Circumstances for Informed Consent.

Incapacitated individuals, defined as persons who are mentally ill, mentally handicapped, or individuals without legal authority, are excluded from the study population. Individuals under the age of 18 or age of legal consent are excluded from the study population. Individuals unable to read or write are excluded from the study population. Pregnant or breastfeeding women are excluded from the study population. All other aspects of the Informed Consent process will be in compliance with [Section 5.2.2]

In addition, an authorization for use and disclosure of the subject's protected health information, in accordance with the Health Insurance Portability and Accountability Act (HIPAA), must be obtained from the subject.

5.3 Eligibility Criteria

5.3.1 General Eligibility Criteria

Assessment for general eligibility criteria is based on medical records of the site and interview with a candidate patient. If some of the clinical and laboratory tests are not included in site standard tests, they must be done after written informed consent is obtained. Patients must meet ALL inclusion criteria to be considered for the clinical investigation. If ANY of the exclusion criteria are met, the patient is excluded from the clinical investigation and cannot be enrolled.

5.3.1.1 Inclusion Criteria

- 1. Patient must provide written informed consent prior to any clinical investigation related procedure.
- 2. Patient has a spinal cord stimulator implanted for chronic, intractable pain.
- 3. Patient has inadequate pain relief from their current SCS system.
- 4. Patient has a pain NRS \geq 6.
- 5. Physician has determined that the patient's original pain is still addressable with neurostimulation.

5.3.1.2 Exclusion Criteria

- 1. Patient is enrolled, or intends to participate, in a competing clinical study, as determined by Abbott.
- 2. Patient is seeking care for a new pain complaint outside of the original indication for SCS.
- 3. Presence of other anatomic or comorbid conditions, or other medical, social, or psychological conditions that, in the Investigator's opinion, could limit the patient's ability to participate in the clinical investigation or to comply with follow-up requirements.
- 4. Physician has determined that patient's pain relief is inadequate due to a malfunction or damage to the existing system.
- 5. Patient requires frequent MRI.
- 6. Patient is involved in active disability litigation related to their pain or seeking worker's compensation.
- 7. Patient is a member of a vulnerable population (See Section 5.2.2.1).

5.4 Subject Enrollment

A patient is considered enrolled in the clinical investigation from the moment the patient provides written informed consent and has been confirmed to meet all eligibility criteria.

Any subject enrolled into the clinical investigation who is later found not to meet all eligibility criteria, will be evaluated by the study team. If the deviation is found to violate the scientific integrity of the study or unduly influence the study aims, the subject will be withdrawn from the study. Otherwise, the subject will continue in the study and be included in the analysis population.

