5.5 Subject Deregistration

Subjects are considered deregistered if a study device was not introduced to the subject for any reason (e.g., payor denial or inability to place leads), and are excluded from the analysis set.

The Full Analysis Set (FAS) is the analysis set which is as complete as possible and as close as possible to the intention-to-treat ideal of including all enrolled subjects. Deregistered subjects will be excluded from the FAS, but must be followed and documented according to the CIP requirements until they withdraw informed consent.

Subjects who are deregistered or discontinued for the above-mentioned reasons will not count towards the total sample size.

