5.6 Subject Withdrawal

Each enrolled subject shall remain in the clinical investigation until completion of the required follow-up period; however, a subject's participation in any clinical investigation is voluntary and the subject has the right to withdraw at any time without penalty or loss of benefit. Conceivable reasons for discontinuation may include, but not be limited to, the following:

- Subject death
- Subject voluntary withdrawal
- Subject lost-to follow-up as described below
- Subject's follow-up is terminated (per Section 3.3)
- Subject's neurostimulation system has been explanted

The Sponsor must be notified of the reason(s) for subject discontinuation. The site will provide this information to the Sponsor. Investigators must also report this to their respective IRB/EC as defined by their institution's procedure(s).

No additional follow–up will be required or data recorded from subjects once withdrawn from the clinical investigation, except for the status (deceased/alive).

However, if a subject withdraws from the investigation due to problems related to the safety or performance of the device under investigation, the Investigator shall ask for the subject's permission to follow his/her status/condition outside of the clinical investigation.

In case of subject withdrawal of consent, the site should make attempts to schedule the subject for a final clinical investigation visit.

Lost-to-Follow-up

If the subject misses two consecutive scheduled follow-up time points, and the attempts at contacting the subject detailed below are unsuccessful, then the subject is considered lost-to-follow-up. Site personnel shall make all reasonable efforts to locate and communicate with the subject (and document these efforts in the source documents), including the following, at each contact time point:

- A minimum of two telephone calls on different days over the specified follow-up windows to contact the subject should be recorded in the source documentation, including date, time and initials of site personnel trying to make contact.
- If these attempts are unsuccessful, a letter (certified if applicable) should be sent to the subject.
- If a subject misses one or more non-consecutive follow-up contact time points, it will be considered a missed visit. The subject may then return for subsequent visits. If the subject misses

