8.1 Analysis Populations

The Full Analysis Set (as defined in Section 5.5) will be the analysis population.

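### Protocol 5.4 allows discretionary withdrawal of subjects later found ineligible, with no time limit or masking to outcomes, and does not fit the Full Analysis Set in 5.5 and 8.1

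*Protocol*

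**What the plan says.** Protocol 5.4 sets the trigger: "Any subject enrolled into the clinical investigation who is later found not to meet all eligibility criteria, will be evaluated by the study team". It then gives two outcomes. The first is withdrawal: "If the deviation is found to violate the scientific integrity of the study or unduly influence the study aims, the subject will be withdrawn". The second is retention: "Otherwise, the subject will continue in the study and be included in the analysis population". The section does not say by when the evaluation must happen, who forms the study team, which deviations qualify, or what the evaluators may know about the subject's results.

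Protocol 8.1 fixes the population: "The Full Analysis Set (as defined in Section 5.5) will be the analysis population". Protocol 5.5 describes that set as "as close as possible to the intention-to-treat ideal of including all enrolled subjects" and names one exclusion: "Deregistered subjects will be excluded from the FAS". Deregistered means that no study device was introduced.

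Under protocol 5.6, no further follow-up is required and no "data recorded from subjects once withdrawn from the clinical investigation", with vital status the only exception. SAP 3.3 summarises early terminations, withdrawals included, for subjects in the FAS. SAP 2.3.1 tests six endpoints in a fixed order at the 0.05 level, all of them changes from baseline to 6 months.

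**The concern.** Once a subject is known to be ineligible, the breach is already established. What 5.4 then asks is whether the deviation would distort the study's aims, and protocol 2.1 gives restored pain relief as one of those aims. That question is hard to separate from how the subject fared when the study is open-label and the question can be put at any time.

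The only independent body described, the Clinical Events Committee, adjudicates adverse events and not eligibility. Several criteria in protocol 5.3.1 rest on opinion: whether the original pain is still addressable, whether a psychological or social condition could limit participation, and whether the old system had malfunctioned. Such criteria can be re-read after a poor response.

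If withdrawals followed poor results, the mean changes tested in SAP 2.3.1 would lean towards the device. Adverse event follow-up would also be cut short, because safety surveillance ends at withdrawal (protocol 7.3.1). Without a control group, nothing inside the study would reveal the lean.

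**Working it through.** **1. The passages side by side.** The effect of a 5.4 withdrawal depends on when it happens.

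| Time of withdrawal | Protocol 5.4 (implied) | Protocol 5.5 and 8.1, SAP 3.3 | 6-month change score |
|---|---|---|---|
| Before a study device is introduced | Not analysed | Deregistered, not in FAS | None; the sections agree |
| After introduction, before the 6-month visit | Not analysed | In FAS | Lost on either reading, because 5.6 stops data collection |
| After the 6-month visit | Not analysed | In FAS | Recorded; lost only if 5.4 governs |

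The disagreement is therefore confined to subjects in whom a device was introduced. In the middle row, nominal membership of the FAS does not restore the missing score.

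**2. Size, for scale only.** The planned 100 subjects (protocol 5.7) is the only relevant figure in the documents. Its inputs are not in the available text, so it is not reproduced, and the point does not depend on it.

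Assumptions:
- n = 100, normal change scores with true mean change 0
- SD of NRS change 2 to 3 points
- one-sample t-test, two-sided 0.05, so nominally 0.025 in favour of the device
- k ineligible subjects

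Case A (extreme): the k ineligible subjects are the k worst outcomes, and all are removed. With p = k/100, the shift in SD units is roughly φ(z_p)/(1 − p). For k = 5, z = −1.645 and φ = 0.1031, so 0.1031/0.95 = 0.109.

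Case B (milder): the k ineligible subjects are a random set, and only those with no improvement are removed. Each is removed with probability 1/2, so the shift is roughly k × 0.399/(100 − k/2). For k = 5, 5 × 0.399/97.5 = 0.020.

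A simulation of 40,000 trials gave the following. FP is the false-positive rate in favour of the device, and the points columns multiply the shift by 2 and by 3.

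| k | A: shift (SD) | A: NRS points | A: FP | B: shift (SD) | B: NRS points | B: FP |
|---|---|---|---|---|---|---|
| 1 | 0.026 | 0.05–0.08 | 0.049 | 0.004 | about 0.01 | 0.026 |
| 3 | 0.069 | 0.14–0.21 | 0.121 | 0.012 | 0.02–0.04 | 0.032 |
| 5 | 0.107 | 0.21–0.32 | 0.228 | 0.020 | 0.04–0.06 | 0.038 |
| 10 | 0.193 | 0.39–0.58 | 0.564 | 0.042 | 0.08–0.13 | 0.057 |

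The formulas agree with the simulated shifts. With nothing removed, the simulated rates were 0.026 (A) and 0.023 (B), so the B result for k = 1 cannot be told from nominal.

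**The case against.** The strongest reply is that 5.4 speaks of withdrawal from the study, not removal from the analysis. Protocol 5.5 and 8.1 define the analysis set, and SAP 3.3 plainly expects withdrawn subjects within it. On that reading, data recorded before withdrawal are kept. This has force: exclusion is implied by the retention sentence and nowhere stated. SAP 2.1.1, which should define the FAS, appears only as a heading in the available text and may settle the matter. That gap is not counted against the plan. The reading does not help a subject withdrawn before the 6-month visit, whose tested score is never collected.

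A reader might go further and infer that the sponsor means to drop treated subjects who do badly, or that the tested results are biased. The documents support neither. The rule reaches only subjects who breach a criterion, including those found before implant. It is the deviation that is judged, and many criteria are baseline facts, such as NRS of at least 6 or active litigation. The study team is undefined, so its access to outcomes is not described either. Before month 6 the tested outcome is still unknown, although end-of-trial and 3-month scores could hint at it.

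Some transparency already exists. Deviations go on a dedicated form (protocol 10.6), discontinuation reasons go to the sponsor and IRB/EC (5.6), and the SAP summarises both. This would show that withdrawals happened, but it would not restore the data. The safety follow-up offered in 5.6 is for subjects who themselves withdraw over device safety or performance, not for removal by the study team.

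**Conclusion.** The point holds as a rule that permits outcome-aware exclusion and as an unreconciled difference between sections. It does not hold as a demonstrated bias or a flat contradiction. The time-unlimited, undefined judgement in 5.4 and the loss of data under 5.6 stand on the text alone. The implied exclusion from analysis stands unless the SAP's FAS definition says otherwise. The absence of a control group is inferred from the lack of randomisation (SAP 1.5) and of any described comparator.

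The likely size is small with few ineligible subjects and becomes material only with several, strongly selected withdrawals. For 5 in 100 the range runs from Case B, with a false-positive rate of about 0.038 against 0.025, to Case A, at about 0.23. The documents give no expected rate of late-found ineligibility, so these are bounds under assumption and not a forecast. The rule should be corrected because the remedy is cheap and matches the plan's own intention-to-treat aim.

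**What to change.** - In protocol 5.4, state that any subject in whom a study device was introduced stays in the FAS whatever is later learned about eligibility, and continues follow-up where valid consent and IRB/EC requirements allow. The proviso matters because some breaches concern consent itself or membership of a vulnerable population (protocol 5.3.1).
- Align 5.4 with 5.5 and with the FAS definition in SAP 2.1.1, so that all three give the same membership rule.
- Add to the SAP one sensitivity analysis of the tested endpoints that excludes ineligible subjects, identified from pre-treatment data only by people without access to outcomes.

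Cost: a few ineligible subjects remain in the main analysis, and one table is added. The protocol change needs a routine amendment, with written IRB/EC acknowledgement or approval before it takes effect (protocol 10.3 and 12.1), at up to 40 sites.
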